2.2. Visit Windows

Nominal visits will be used for all by-visit analyses in the study. The study visits scheduled post randomization should occur at the times delineated in the Schedule of Activities. The study visits through Week 36 should occur within ± 7 days of the scheduled visit. The sponsor must be contacted for any significant deviation in the scheduling of a visit outside the appropriate window and determine how the subject should resume his/her normal dosing schedule relative to the baseline visit (Week 0).

2.3. Pooling Algorithm for Analysis Centers

Unless otherwise specified, data from all investigational centers/sites will be pooled for analyses.

2.4. Analysis Sets

There will be at least two database locks at Weeks 16 and 48 respectively, but additional locks may be performed.

Week 16 database lock

Week 16 database lock will include all data through Week 16 for all randomized participants. In addition, the available data through Week 48 by the time the last participant completes Week 16 visit will also be included. The additional data will be primarily used to assess the maintenance of clinical response through week 48 in planning for future clinical development in HS; selected efficacy, safety, and PK/PD analyses (Section 5.5, 6.1, and 7.1.1) with the data through Week 48 will be included in Week 16 database lock.

Week 48 database lock

Week 48 DBL would include all data through Week 48 for all randomized participants.

2.4.1. Efficacy Analysis Set(s)

2.4.1.1. Full Analysis Set

The full analysis set (FAS) includes all randomized participants who received at least 1 dose (complete or partial) of study agent. This analysis set will be used for the efficacy analyses of the endpoints through Week 48, *unless otherwise specified*.

In the efficacy analyses, participants will be analyzed according to the randomized treatment groups they were assigned to, regardless of the treatments they actually received.

2.4.1.2. Per Protocol Analysis Set

The primary endpoint will also be analyzed using the per-protocol population, which includes participants who are generally compliant with the protocol.

Specifically, the per protocol population includes participants in FAS except those

- who did not meet the inclusion criteria 6 in the protocol as listed below:
 - Have a total abscess and inflammatory nodule (AN) count of ≥ 3 at the screening and baseline.
- who met the exclusion criteria 2 in the protocol as listed below:
 - Has a draining fistula count of >20 at the baseline visit.
- who did not complete the specified exposure to study agent as outline below
 - participants randomized to placebo at Week 0 who received guselkumab prior to Week 16.
 - participants randomized to guselkumab 1200 mg at Week 0 but did not receive all scheduled guselkumab administrations prior to Week 16.
 - participants randomized to guselkumab 200 mg at Week 0 but did not receive all scheduled guselkumab administrations prior to Week 16.

However, for those who did not complete the specified exposure to study agent as outline above, participants who discontinued the study agent due to unsatisfactory therapeutic effect (lack of efficacy) or an adverse event (AE) of worsening of HS, or participants who started prohibited medications and continued receiving study agents prior to the specified timepoint for the endpoints will be included in the per protocol analysis and the treatment failure rules specified in Section 5.2.3.2 will apply.

Participants who were excluded from the per protocol analyses will also be summarized.

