Participants who decide to discontinue study intervention administration for reasons other than those outlined above must be interviewed by the investigator to determine if a specific reason for discontinuing study intervention can be identified. Participants should be explicitly asked about the possible contribution of AEs to their decision to discontinue study intervention; investigators should confirm that any AE information elicited has been documented. If a participant elects to discontinue study intervention due to an AE, the event should be recorded as the reason for study intervention discontinuation, even if the investigator's assessment is that the AE would not require study intervention discontinuation. The reason for study intervention discontinuation must be documented in the eCRF and in source documents. Study intervention assigned to a participant who discontinues may not be assigned to another participant.

A participant will not be automatically withdrawn from the study if he or she must discontinue treatment before the end of the treatment regimen. Participants who discontinue study intervention but do not terminate study participation will continue to return for protocol-specified procedures and evaluations for approximately 12 weeks following the last dose of study intervention. The procedures and evaluations listed for the Early Termination Visit should also be performed approximately 12 weeks after the last dose of study intervention.

All procedures and evaluations must be conducted prior to a participant's withdrawal of consent.

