5.2.3.3.1. Missing Data Binary Endpoints

For binary efficacy endpoints, participants with missing response status will be considered non-responders for all of the efficacy analyses at key visit of Week 16 and over time summaries.

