5.3.2. Analysis Methods

The primary endpoint will be compared between the each guselkumab group and the placebo group. The primary endpoint will be analyzed at Week 16 based on the composite estimand (Section 5.2.4.1) and the data from all participants in FAS (Section 2.4.1.1) will be analyzed according to randomized treatment group regardless of the treatment actually received.

Participants who meet treatment failure criteria prior to Week 16 will be considered nonresponders for the primary endpoint at Week 16. In addition, participants who do not return for evaluation at Week 16 will be considered nonresponders at Week 16.

In this primary analysis, the number and proportion of participants who achieve a HiSCR at Week 16 will be summarized for each treatment group. To address the primary objective, a CMH chi-square statistic stratified by baseline weight (≤ 95 kg, >95 kg) and baseline Hurley stage status at an alpha level of 0.05 will be used for each of the following hypotheses:

1. Guselkumab 1200 mg IV versus placebo in HiSCR at Week 16.
2. Guselkumab 200 mg SC versus placebo in HiSCR at Week 16.

The study is considered positive if at least one of the hypotheses is tested as significant.

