5.3.4. Sensitivity Analysis

Sensitivity Analysis 1

For participants who do not return for evaluation at Week 16, the analysis will be performed using observed data after applying treatment failure rules (as defined in Section 5.2.3.2).

Sensitivity Analysis 2

A second sensitivity analysis will be performed by using multiple imputations (MI) by treatment group based HiSCR responses respectively. The fully conditional specification (FCS) method will be used to impute the missing data after applying treatment failure for the HiSCR response at Week 16.

More specifically, the missing HiSCR response status will be imputed using FCS method with 50 imputed data sets with seed = 1231 to fill in the missing HiSCR responses through Week 16 in each of the 50 copies of datasets. The proportion difference of HiSCR at Week 16 adjusted for baseline weight (≤ 95 kg, >95 kg) and baseline Hurley stage using Mantel-Haenszel weight between the guselkumab groups and the placebo group and its 95% CI combining multiple datasets will be provided. In addition, the p-value for testing the treatment difference will be obtained from SAS PROC MIANALYZE based on these combined Mantel-Haenszel estimates from the multiple imputation datasets.

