5.3.6. Per-protocol Analysis

The primary analyses for primary endpoint will also be performed on per-protocol analysis set (Section 2.4.1.2). Similar treatment failure rules and data handling rules specified in Section 5.2.3 will apply.

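### The per-protocol set requires complete dosing before Week 16 in both guselkumab arms but not in placebo, so the per-protocol HiSCR comparison selects on adherence in only two of three arms

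*SAP*

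**What the plan says.** SAP 2.4.1.2 starts from the FAS and removes participants who fail the AN-count criterion, exceed the draining-fistula limit, or did not complete the specified exposure. The exposure condition is then written separately for each arm:

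- **Guselkumab 1200 mg:** exclude "participants randomized to guselkumab 1200 mg at Week 0 but did not receive all scheduled guselkumab administrations prior to Week 16". The 200 mg arm has the same rule.
- **Placebo:** exclude "participants randomized to placebo at Week 0 who received guselkumab prior to Week 16".

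An exception returns incomplete dosers who stopped for lack of efficacy or an adverse event of worsening HS, and participants who started prohibited medication while continuing study agent. The treatment failure rules then apply to them. The section adds: "Participants who were excluded from the per protocol analyses will also be summarized".

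SAP 5.3.6 uses the set as follows: "The primary analyses for primary endpoint will also be performed on per-protocol analysis set", with similar data handling rules. Under SAP 5.2.3.3.1, "participants with missing response status will be considered non-responders". Under SAP 5.3.2, "participants who do not return for evaluation at Week 16 will be considered nonresponders at Week 16".

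**The concern.** The active-arm condition tests completion. The placebo condition tests contamination. Placebo participants also have scheduled study agent at Weeks 0, 4, 8 and 12 (SAP 1.2), yet no line deals with missed placebo doses. One dose, even a partial one, puts a participant in the FAS (SAP 2.4.1.1), so a placebo participant with a single dose can remain in a set meant for people who broadly followed the protocol.

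Missed doses mark dropout as well as lower exposure, and dropout leads to non-responder imputation. If the rule removes those participants from guselkumab and keeps them in placebo, part of any larger per-protocol difference comes from the rule itself. A reader could take that part as evidence that fuller exposure works better.

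**Working it through.** **Who is affected.** Each guselkumab arm has four guselkumab administrations scheduled before Week 16 (Weeks 0, 4, 8 and 12). Missing any one of them, for a reason outside the exception, removes the participant. The same behaviour on placebo does not.

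**Who lacks Week 16 data.** Protocol 7.1 says that those who stop treatment but stay in the study "will continue to return for protocol-specified procedures and evaluations for approximately 12 weeks following the last dose of study intervention". Counting 12 weeks from the last dose:

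- Last dose at Week 0: follow-up ends at about Week 12, before the endpoint.
- Last dose at Week 4: about Week 16.
- Last dose at Week 8: about Week 20.

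Under this rule, only those who stop after Week 0 finish before the endpoint, and not all of them: Protocol 6.3 and 8.2.11.2 ask participants unblinded by the investigator, and those who stop latent TB treatment early, to keep attending. Withdrawals and losses to follow-up add to the group without Week 16 data. Someone who skips one visit and continues can have an observed result.

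**Inputs.** The plan gives 60 participants per arm, a placebo HiSCR rate of about 25% and a difference of about 30 points (Protocol 9.2, SAP 1.4). It states no figure for the per-protocol set. As a check on the inputs, a pooled normal approximation gives 84.1%, 94.1%, 98.4%, 81.6%, 92.9% and 98.0% power for the six rows of Table 1, against the stated 85%, 94%, 98%, 82%, 93% and 98%.

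Two quantities are assumptions:

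- q, the share of each arm with missed doses outside the exception: 5%, 10% or 20% (3, 6 or 12 of 60).
- r, the Week 16 response rate of those participants.

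**Bias with no true effect.** Let R = 0.25 be the full-arm rate in both arms. The per-protocol rate is (R − q·r)/(1 − q) in guselkumab and stays at R in placebo. The spurious difference is q(R − r)/(1 − q).

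| r | q = 5% | q = 10% | q = 20% |
|---|---|---|---|
| 0 (upper bound) | +1.3 | +2.8 | +6.3 |
| 0.15 | +0.5 | +1.1 | +2.5 |
| 0.25 | 0 | 0 | 0 |
| 0.40 | −0.8 | −1.7 | −3.8 |

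Values are percentage points. For example, at q = 10% and r = 0: 0.10 × 0.25/0.90 = 0.028. If 25% is instead the rate among adherent participants, the bias is q(0.25 − r), which at r = 0 gives 1.25, 2.5 and 5.0 points.

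The standard error of a difference with 60 per arm is √(2 × 0.25 × 0.75/60) = 0.079. At q = 5% the upper bound is 0.0132/0.079 = 0.17 of it.

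**Rejection rates.** These come from exact binomial enumeration of an unstratified pooled z-test with critical value 1.96, R = 0.25 as the full-arm rate and r = 0, comparing 57, 54 or 48 guselkumab with 60 placebo participants.

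| | q = 5% | q = 10% | q = 20% |
|---|---|---|---|
| Favouring guselkumab, SAP rule | 3.8% | 5.6% | 11.8% |
| Two-sided total, SAP rule | 5.4% | 6.7% | 12.2% |
| Favouring guselkumab, same rule in both arms | 2.6% | 2.5% | 2.6% |

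With r = 0.15 the first row becomes 3.0%, 3.6% and 5.4%.

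**At the planned effect.** Take full-arm rates of 55% and 25%, q = 10% and r = 0:

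- SAP rule: 0.55/0.90 − 0.25 = 36.1 points.
- Same rule in both arms: (0.55 − 0.25)/0.90 = 33.3 points.
- FAS: 30 points.

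Of the 6.1 points above the FAS, 36.1 − 33.3 = 2.8 come from the asymmetry. The other 3.3 come from per-protocol conditioning itself.

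**The case against.** **No decision rests on this analysis.** Success is defined on the FAS, none of the eight tested hypotheses is per-protocol, and the SAP attaches no alpha or interpretive rule to the result. This stands and limits the weight of the point.

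**r = 0 is a worst case.** The exception already keeps the participants most clearly destined to be non-responders, and those who stop after Week 4 or Week 8 should still be seen at about Week 16. This also stands. The r = 0 figures are a ceiling, and for participants with observed Week 16 data the direction is open.

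**One-sided error rates look larger than they are.** The plan tests two-sided at 0.05. At q = 5% and r = 0 the exact two-sided rate is 5.4%, a small change. The inflation matters only at larger q.

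**The rule can be read as defining guselkumab exposure:** none in placebo, all scheduled doses in the active arms. That is coherent for pharmacology but does not make the arms comparable. A missed placebo dose leaves drug exposure unchanged, yet it still marks dropout, and dropout determines who is imputed as a non-responder.

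**Other safeguards exist.** For participants who do not return at Week 16, Sensitivity Analysis 1 in SAP 5.3.4 specifies that "the analysis will be performed using observed data after applying treatment failure rules", and a second analysis uses multiple imputation. Both treat missing Week 16 data alike in every arm and give the reader a check on the FAS result. They do not correct the per-protocol estimate.

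**Conclusion.** The concern holds. The exposure rule differs by arm, and neither the exception nor any other section restores balance. Among participants who miss doses for reasons outside the exception and have no Week 16 assessment, the bias favours guselkumab. For those who do attend Week 16 it may be positive, zero or reversed.

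With no true effect and 25% response, the size runs from 0 to at most 1.3, 2.8 or 6.3 points in favour of guselkumab at q = 5%, 10% or 20%. It reverses by 0.8, 1.7 or 3.8 points if affected participants respond at 40%. Both q and r are assumptions, because the documents supply neither.

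The consequence is confined to a supplementary analysis. The change is worth making because it is cheap and removes an avoidable ambiguity in how a per-protocol result would be read.

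**What to change.** In SAP 2.4.1.2, replace the three arm-specific lines with one exposure rule for all arms: exclude participants who did not receive every scheduled blinded study agent administration, active or placebo, before Week 16, or who received a treatment other than the one assigned. Apply the same treatment failure exception in each arm. Break down the already planned summary of per-protocol exclusions by arm and reason.

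This is one rule change and needs no new data. The double-dummy schedule gives every arm the same visits, missed administrations are already listed by randomized group (SAP 4.5), and reasons for stopping study agent are already summarized by group (SAP 4.2). Only the arm-by-reason breakdown is new.

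The cost is a smaller set. It loses guselkumab participants who had every active dose but missed a dummy one (SC placebo in Group 1, IV placebo in Group 2), and placebo participants whose missed dose did not change guselkumab exposure. The set also remains a post-randomization subset that will not reproduce the FAS estimate, as the 33.3 against 30 points above shows.

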2.4.2. Safety Analysis Set

The safety analysis set includes all randomized participants who received at least 1 (partial or complete) dose of study agent, i.e., the treated population.

In the safety analyses, participants will be analyzed according to the treatment they actually received, regardless of the treatments they are randomized to.

2.4.3. Pharmacokinetics Analysis Set

The pharmacokinetic (PK) analysis set includes all participants who received at least 1 complete dose of guselkumab and had at least 1 valid blood sample drawn for PK analysis after their first dose of guselkumab.

In the PK analyses, participants will be analyzed according to the treatment they actually received, regardless of the treatments they are randomized to.

2.4.4. Immunogenicity Analysis Set

The immunogenicity analysis set includes all participants who received at least 1 (partial or complete) dose of guselkumab and who have at least 1 sample obtained after their first dose of guselkumab for the detection of antibodies to guselkumab.

In the immunogenicity analyses, participants will be analyzed according to the treatment they actually received, regardless of the treatments they are randomized to.

2.5. Definition of Subgroups

To evaluate the consistency in the primary efficacy endpoint (proportion of participants who achieve HiSCR at Week 16) over demographics, baseline characteristics, prior and baseline medication use, subgroup analyses will be performed when sample sizes are permitted. The subgroups include, but are not limited to, the following:

Baseline demographics:

- Sex (male, female)
- Race
- Baseline Age (<40 years, 40 to <65 years, ≥65 years)
- Baseline weight (≤95 kg, >95 kg)
- BMI (Normal [<25], Overweight [$25 - <30$], Obese [≥ 30])

Baseline disease characteristics:

- Baseline Hurley stage status (I, II, and III)
- Age at diagnosis (years) (< median, ≥ median)
- HS disease duration (years) (< median, ≥ median)
- Baseline high-sensitivity C-reactive protein (hs-CRP) (< median, ≥ median)
- Baseline AN count category (3 to 5, 6 to 10, ≥11)
- Baseline AN count (< median, ≥ median)
- Baseline HS-IGA (<3, 3, 4)

HS medication and surgery history:

- Systemic immunomodulatory biologics (adalimumab, infliximab, other-anti-TNF inhibitors, ustekinumab)
 - Never used
 - Ever Used

- Hidradenitis Suppurativa related surgery (Deroofing Surgery, Laser Surgery, Excision Surgery)
 - Never had
 - Ever had

2.6. Study Day and Relative Day

Study day is defined as the number of days from the study reference date to the event/visit date. It will be calculated as follows:

- If the event/assessment occurs on or after the reference date, then study day = event/assessment date – reference date + 1.
- If the event/assessment occurs before the reference date, then study day = event/assessment date – reference date.

Hence, the day of reference date is Study Day 1; the previous day is Study Day -1.

2.7. Baseline and Endpoint

In general, the baseline measurement is defined as the closest measurement taken prior to or at the time of the first study agent administration date unless otherwise specified.

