1.2. Trial Design

This is a Phase 2, multicenter, randomized, placebo-controlled, double-blind, proof-of-concept (POC) study evaluating the efficacy, safety, PK, and immunogenicity of SC and IV administered guselkumab for the treatment of moderate to severe HS in adult participants. The participant population will comprise men and women who have had moderate to severe HS for at least 1 year.

A diagram of the study design ([Figure 1](#)) is provided below and as depicted in [Figure 1](#), approximately 180 participants who satisfy all inclusion and exclusion criteria will be randomized in a 1:1:1 ratio to 1 of 3 groups:

Group 1: Guselkumab Regimen 1 (1200 mg IV q4w x 3 → 200 mg SC q4w)

Participants will receive guselkumab 1200 mg IV at Week 0, Week 4, and Week 8 (ie, a total of 3 IV guselkumab doses and 3 SC placebo doses). At Week 12, participants will continue treatment with guselkumab 200 mg SC q4w through Week 36.

Group 2: Guselkumab Regimen 2 (200 mg SC q4w x 3 → 200 mg SC q4w)

Participants will receive guselkumab 200 mg SC at Week 0, Week 4, and Week 8 (ie, a total of 3 SC guselkumab doses and 3 IV placebo doses). At Week 12, participants will switch treatment to guselkumab 200 mg SC q4w through Week 36.

Group 3: Placebo

[figure not shown]
Participants will receive placebo IV and SC at Week 0, Week 4, and Week 8 (ie, a total of 3 IV and 3 SC placebo doses) and an additional SC placebo dose at Week 12. At Week 16, participants will be rerandomized in a 1:1 ratio to either guselkumab 200 mg SC q4w through Week 36 or guselkumab 100 mg SC at Weeks 16, 20, 28, and 36, and placebo at Weeks 24 and 32.

A screening period will take approximately 4 weeks. All participants will enter safety follow-up after Week 36 through Week 48. Two planned database locks (DBLs) will occur, at Week 16 and at Week 48.

Efficacy assessments (HS-IGA, lesion counts, Hurley staging, Hidradenitis Suppurativa Symptom Diary [HSSD], Dermatology Life Quality Index [DLQI], Hospital Anxiety and Depression Scale [HADS], and Patient's Global Impression of Change [PGIC]) will be performed according to the Schedules of Activities. Serum samples for PK, immunogenicity, and biomarker analyses will be collected at the timepoints shown in the Schedules of Activities (Section 1.3 of the protocol).

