4.4. Extent of Exposure

The exposure data through Week 16 and through Week 36 will be summarized. The number and percentage of participants who receive study agent will be summarized by treatment group for the safety analysis set. Descriptive statistics will be presented for the following parameters:

- Number of administrations
- Cumulative total dose

Study agent lots received by treatment, including matching placebo for active treatment will be summarized.

In addition, the average exposure (number of administrations) and average duration of follow-up (weeks) will also be summarized by treatment group in the safety tables through different study time periods.

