2. **Placebo → guselkumab 100 mg SC:** all participants who were randomized to placebo at Week 0 started treatment with placebo only and later randomized to treatment with guselkumab 100 mg SC q8w. Only the safety events/measurements from these participants that occurred on and after their first administration of guselkumab will be included in this group.
3. **Placebo → guselkumab 200 mg SC:** all participants who were randomized to placebo at Week 0 started treatment with placebo only and later randomized to treatment with guselkumab 200 mg SC q4w. Only the safety events/measurements from these participants that occurred on and after their first administration of guselkumab will be included in this group.
4. **Guselkumab 200 mg SC:** all participants who were randomized to guselkumab 200 mg SC q4w at Week 0 and received guselkumab. All the safety events/measurements from these participants that occurred from Week 0 will be included in this group.
5. **Guselkumab 1200 mg IV:** all participants who were randomized to guselkumab 1200 mg IV q4w at Week 0 and received guselkumab. All the safety events/measurements from these participants that occurred from Week 0 will be included in this group.

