6.2. Clinical Laboratory Tests

All clinical laboratory reports will be displayed for the participants included in the safety analysis set. The clinical laboratory parameters to be evaluated by the central laboratory include but are not limited to:

- **Hematology:** hemoglobin, hematocrit, lymphocytes, neutrophils, platelets, red blood cell (RBC) count and white blood cell (WBC) count.
- **Chemistry:** albumin, alkaline phosphatase, alanine aminotransferase, aspartate aminotransferase, total bilirubin, blood urea nitrogen/urea, calcium, chloride, creatinine, glucose, potassium, total protein, sodium.

Box plots of laboratory measurements and change from baseline will be provided for the selected laboratory measurement.

Applicable laboratory results will be graded according to National Cancer Institute's Common Terminology Criteria for Adverse Events (NCI-CTCAE version 5.0). The worst NCI-CTCAE will be summarized by treatment group.

For non-fasting glucose, the screening measurement will be used as the baseline measurement. A listing of participants with 1 or more NCI-CTCAE toxicity grade ≥ 2 in hematology and clinical chemistry laboratory measurements will be provided

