6.3. Vital Signs and Physical Examination Findings

Vital signs variables including heart rate and blood pressure (systolic and diastolic) will be measured at visits as per the schedule of activities in the protocol. Descriptive statistics of the observed value and change from baseline of the vital signs will be summarized by treatment group.

Physical exam findings will not be analyzed. When physical exam findings are captured as AEs, those will be included in the analyses of AEs.

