6.4. Other Safety Parameters

Weight and Waist Circumference

Descriptive statistics of changes from baseline will be summarized at selected scheduled time points.

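### In the two placebo-to-guselkumab safety columns, change from baseline in laboratory values, vital signs and weight starts at Week 0 and so includes the placebo period

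*SAP*

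**What the plan says.** SAP 2.7 gives the general rule: "the baseline measurement is defined as the closest measurement taken prior to or at the time of the first study agent administration date", unless another rule is specified. Study agent covers placebo as well as guselkumab. SAP 4.4 shows this: "Study agent lots received by treatment, including matching placebo for active treatment will be summarized".

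Placebo-randomized participants first receive guselkumab at Week 16. SAP 1.2 says: "At Week 16, participants will be rerandomized in a 1:1 ratio to either guselkumab 200 mg SC q4w through Week 36", the alternative being the 100 mg SC regimen.

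SAP 6 defines both placebo-to-guselkumab safety columns with the same restriction: "Only the safety events/measurements from these participants that occurred on and after their first administration of guselkumab will be included in this group". It does not redefine baseline for them. It presents the Week 48 layout, which also has a Combined Guselkumab column, as allowing safety comparison between the guselkumab regimens.

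Three sections then plan change from baseline:
- Laboratory values, SAP 6.2: "Box plots of laboratory measurements and change from baseline will be provided for the selected laboratory measurement".
- Vital signs, SAP 6.3: "Descriptive statistics of the observed value and change from baseline of the vital signs will be summarized by treatment group".
- Weight and waist circumference, SAP 6.4: "Descriptive statistics of changes from baseline will be summarized at selected scheduled time points".

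The safety sections specify two other baselines. One is in SAP 6.2: "For non-fasting glucose, the screening measurement will be used as the baseline measurement". The other, in SAP 6.5, takes the worse of the screening and Week 0 scores for the C-SSRS. Neither moves baseline to Week 16.

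**The concern.** The crossover columns run on two clocks. A measurement qualifies by its timing relative to first guselkumab, but its change is counted from first placebo. These columns stand beside the 200 mg SC and 1200 mg IV columns, where all the time since baseline is time on the guselkumab regimen. A reader comparing regimens will naturally take the crossover figures as change on guselkumab.

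Any systematic movement in weight, blood pressure or a laboratory value during the placebo period is therefore shown under a guselkumab regimen. The 100 mg regimen is the most exposed: it exists only as a crossover column, so no change display for it is free of placebo time.

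**Working it through.** No figure in the plan has to be reproduced. The check is a reading of the text followed by interval arithmetic.

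**1. Baseline by column.** Week 0 is the first study agent administration for everyone (SAP 2.7, with SAP 4.4). For the 200 mg SC and 1200 mg IV columns that is also the first guselkumab dose. For the two crossover columns, first guselkumab is Week 16 (SAP 1.2).

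**2. What the crossover columns report.** Let *d* be the mean change from Week 0 to Week 16 on placebo, and *g* the mean change from Week 16 to the visit on guselkumab. The planned figure is *d* + *g*. The figure a regimen comparison needs is *g*. The difference is *d*.

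**3. Share of the interval spent on placebo** = 16 / (weeks since Week 0). Assessments are those in the protocol's Schedule of Activities (Section 1.3).

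| Visit | Assessed | Weeks on guselkumab | Placebo share |
|---|---|---|---|
| Week 20 | vital signs | 4 | 16/20 = 80% |
| Week 24 | vital signs | 8 | 16/24 = 67% |
| Week 28 | vital signs | 12 | 16/28 = 57% |
| Week 32 | vital signs | 16 | 16/32 = 50% |
| Week 36 | vital signs | 20 | 16/36 = 44% |
| Week 40 | vital signs, hematology, chemistry | 24 | 16/40 = 40% |
| Week 44 | vital signs | 28 | 16/44 = 36% |
| Week 48 | vital signs, hematology, chemistry, weight | 32 | 16/48 = 33% |

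These are shares of time. They are shares of the change only if change is linear, which nothing in the documents establishes.

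**4. The Week 16 value itself.** SAP 6 assigns measurements on and after first guselkumab to the crossover columns. If that is programmed by calendar date, the pre-dose Week 16 value moves into a guselkumab column, and its change is 16/16 = 100% placebo.

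**5. Combined Guselkumab.** SAP 6 lists this column without defining its contents. Assume that it pools all guselkumab-treated participants and that all 60 planned placebo participants cross over. They are then 60/180 = one third of it, and the column carries *d*/3. Sixty is an upper bound, because only those who go on to receive guselkumab contribute.

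**6. Size of *d*.** The documents give no expected placebo-period change. As an assumption for illustration only, a mean weight change of 0.5 kg (range 0 to 1 kg) would shift the crossover columns by 0.5 kg (0 to 1) and the combined column by 0.5/3 = 0.17 kg (0 to 0.33).

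**7. With a Week 16 pre-dose baseline.** The placebo share is 0% at every later visit. The interval becomes 24 weeks at Week 40 and 32 weeks at Week 48. The value exists: vital signs, weight, hematology and chemistry are all scheduled at Week 16, and footnote c of the Schedule of Activities puts procedures before dosing unless otherwise indicated. Waist circumference is measured only at Week 0 and at Week 48 or early termination, so it cannot be re-baselined.

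**The case against.** The best defence is that a common Week 0 reference is legitimate. It gives every column change since study entry, and the column titles disclose the sequence. The placebo change to Week 16 appears in its own column, and observed vital signs and laboratory measurements are shown too, so a careful reader could roughly separate the two parts. Re-baselining makes the Week 48 change a 32-week change in two columns and a 48-week change in the others. SAP 6 plans no formal safety comparison. SAP 5.5.4 uses a Week 16 baseline for HiSCR in these participants, but as an additional summary that leaves the Week 0 one in place.

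Much of this stands. It supports keeping the Week 0 display if wanted, and it limits the weight of the point. Re-randomization also makes the expected placebo-period change equal in the two crossover columns, so the comparison of 100 mg with 200 mg between them is not biased by it. It does not answer the mismatch with the columns' own definition, which already limits them to the guselkumab period.

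A reader might also infer that the worst-CTCAE-grade summary has the same defect. The documents do not support that. SAP 6.2 summarizes worst grade without reference to baseline in any column, so an abnormality that was already present and persists can count in every guselkumab column. Requiring worsening in the crossover columns alone would make those regimens look safer by construction.

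**Conclusion.** The point holds for change-from-baseline displays of laboratory values, vital signs and weight in the two placebo-to-guselkumab columns, and in part in Combined Guselkumab. Those displays contain the full 16-week placebo-period change: 40% of the interval at Week 40 and 33% at Week 48. Adverse event counts, observed values and worst CTCAE grades are outside it.

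The conclusion assumes that the general rule in SAP 2.7 applies because the safety sections state no exception for these columns. It also assumes that the default columns of SAP 6 apply to the laboratory and weight displays, since SAP 6.2 and 6.4 do not list theirs. It would be going too far to say that the safety conclusions are biased by a known amount. The placebo-period change may be near zero, and nothing in the documents sizes it. This is a worthwhile, inexpensive improvement to descriptive tables.

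**What to change.** Amend SAP 6, with a cross-reference in SAP 2.7, before the Week 48 lock:

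- For the two placebo-to-guselkumab columns, and for those participants' contribution to Combined Guselkumab, present change from the last value before first guselkumab (Week 16, pre-dose) for hematology, chemistry, vital signs and weight.
- Keep the Week 0-based change, if wanted, as a labelled additional display.
- State that the pre-dose Week 16 value belongs to the Placebo column and serves as the crossover baseline.
- Leave the C-SSRS baseline and the screening baseline for non-fasting glucose as specified. Label crossover-column change in glucose and in waist circumference as including the placebo period.
- Make no change to the CTCAE grade summary on this account.
- Footnote that the change interval is shorter in the crossover columns (32 against 48 weeks at Week 48).

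The cost is a few sentences and a little extra programming, with no new data. The price in interpretation is the unequal intervals, which the footnote discloses.
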